#### 4.3 Exclusion criteria (observation part of the study)

A potential subject who meets any of the following criteria will be excluded from participation in this study. Noticeably, these patients should be registered in the database to identify outcomes in this group (observational registration):

- Pathology shows one or more of the following characteristics:
  - A radical en-bloc resection with a free vertical and lateral margin of  $\geq 1$  mm.
  - A poorly differentiated or signet-cell containing adenocarcinoma.
  - Lymphatic or vascular invasion (if this feature is not assessable due to piecemeal resection, no exclusion is done).
  - Tumor budding (only if specifically mentioned in the pathology report)
  - Deep submucosal invasion ( $> 1$  mm).
- Suspicion of dissemination on investigations as mentioned in the inclusion criteria.
- Patients already receiving anti-tumor treatment for another tumor or a synchronous colorectal cancer or patients pretreated with radiotherapy.
- Patients in whom a second-look endoscopy would require major and unacceptable effort and / or resources, for instance clinical admission for bowel preparation, long travel, general anesthesia, difficult to reach polypectomy site. This decision is left to the discretion of the patient and / or treating physician.
- Patient is not planned for surgery or additional full-thickness resection.
- Patient is pregnant.
- Patient does not provide written informed consent or is unable to provide such.

#### 4.4 Sample size calculation

The overarching goal is to investigate whether second-look endoscopic biopsies after resection of a malignant polyp with uncertain pathological completeness can be used as a screening instrument to aid in the clinical decision whether rescue surgery should be performed or not. The specificity of second-look biopsies from the polypectomy site for residual malignancy is estimated to be near 100%, as it is reasonable to state that no person without residual malignancy in the bowel wall is likely to have tumor in second look biopsies, in other words, the false-positive rate will be approximately zero.

Accordingly, sample size calculations will be done on the basis of sensitivity, i.e. the number of patients with positive second-look biopsies divided by the number of patients who do have residual tumor in the resected specimen. We state that sensitivity should be at least 95% to be clinically relevant. A non-inferiority approach can be used to calculate sample size. In that case, the null-hypothesis states that sensitivity is significantly inferior to 95%. Because proof of exact equality to 95% is impossible, a pre-stated margin of non-inferiority of -5% (90% in our study) is accepted.

The distributions of the probabilities belonging to the null- (around  $p = 0.90$ ) and alternative (around  $p = 0.95$ ) hypothesis is binomial but may be approximated by a normal distribution for sample size calculation.

Using the normal approximation, it can be calculated that 184 patients need to be included to achieve a power of 0.80 with and a probability of falsely accepting biopsies as non-inferior ( $\alpha$ ) of 0.05.

Using binomial distributions, it can be shown that 194 patients need to be included to achieve this goal. We will use the latter number for a robust estimate of sample size.

We estimate incomplete data and / or refusal to participate in 1 out of 10 patients invited.

This calculates to a number of 216 patients with residual tumor to be invited. Depending on the prevalence of residual tumor, which is estimated to vary between 10 and 30% (average 20%) of all patients, a total of 1080 patients fulfilling the inclusion criteria need to be invited to accomplish this number.

We aim at participation of all eight Academic Centers and all community hospitals. In case of full participation, approximately 520 patients could be acquired each year. We aim at a maximum inclusion period of four years, but preferably shorter.

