#### 8.1.2 Secondary study parameters

The postoperative mortality of the surgical resection (for the purpose of a possibly incompletely removed malignant polyp), as occurring within 91 days after surgery, irrespective of the cause of death as well as of the relation to the surgery (in order to evaluate competing risks).

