### 8.7 Premature termination of the study

It is possible that at an earlier inclusion stage it may be seem that the sensitivity of biopsies is low. However, a low sensitivity, e.g. 70%, may still be useful as it may substantially reduce the post-test probability to below the probability of postoperative death in high risk groups (this is currently difficult to predict, as it is dependent on the observed prevalence of residual tumor, the sensitivity of the biopsy, and the postoperative mortality in the study group). Thus a low observed sensitivity at an earlier inclusion stage shall be no reason to stop the inclusion prematurely.

It can be contemplated to stop inclusion if the observed sensitivity is very high, “definitely” not inferior to 95%. In that case, the negative predictive value of biopsies is so high that is may seem to be unethical to continue operating on these patients if biopsies show no residual cancer. However, the risk of a false conclusion (type I-error) should be extremely small: we pre-state a probability less than 0.0005. For such limits, table 1 is applicable. Results will be evaluated after every inclusion of 20 patients with residual tumor in biopsy. The study will be stopped if the limit has been reached at two evaluations.

Number of patients with residual cancer at operation	Limit for rejecting the 0-hypothesis with a type I error risk < 0.0005
20	19 (95%) (all are positive)
40	39 (97.5%) (all are positive)
60	59 (98.3%) (all are positive)
80	78 (97,5%)
100	97 (97%)
120	116 (96.67%)
140	135 (96.43%)
160	155 (96.89%)
180	173 (96.11%)

Table 1: numbers of patients with tumor in the resection specimen and observed sensitivity limits at which it can be concluded that sensitivity is no inferior to 95% with a probability of a type I error < 0.0005. If these limits are reached on two evaluation points, the study will be prematurely terminated.

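### Section 4.4 tests sensitivity against 90% after calling 95% the minimum worth having, and the post-test risk that section 8.7 reasons from is not among the study parameters

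*Protocol*

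**What the plan says.** Protocol section 4.4 makes three statements about the bar for sensitivity:

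- A minimum: "We state that sensitivity should be at least 95% to be clinically relevant".
- A null worded against that minimum: "the null-hypothesis states that sensitivity is significantly inferior to 95" per cent.
- A margin below it: "a pre-stated margin of non-inferiority of -5% (90% in our study) is accepted". The null distribution is then placed at 0.90 and the alternative at 0.95.

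The size follows from the last of these: "184 patients need to be included to achieve a power of 0.80" by the normal approximation, with 0.05 as the "probability of falsely accepting biopsies as non-inferior", and then "Using binomial distributions, it can be shown that 194 patients need to be included to achieve this goal". Section 3 says that there is no control group.

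Section 8.7 explains why low interim sensitivity will not stop inclusion: "a low sensitivity, e.g. 70%, may still be useful as it may substantially reduce the post-test probability" to below the probability of postoperative death in high-risk groups. It justifies early stopping for very high sensitivity by the negative predictive value. The Table 1 caption words that conclusion as non-inferiority to 95% with a type I error below 0.0005.

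Section 8.1.2 lists one secondary parameter: "The postoperative mortality of the surgical resection" within 91 days. Sections 2.2 and 10 add further sensitivities, proportions, complications and association tests. None lists the negative predictive value or the post-test probability.

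**The concern.** A non-inferiority margin is normally taken below a reference value, such as the performance of an established test. Here it is taken below the value that the protocol itself calls the minimum. The decision rule can therefore declare success when true sensitivity is under that minimum, and a reader told that biopsies are non-inferior to 95% may believe that the minimum was shown.

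The second part concerns what the trial is for. Section 4.4 gives the overarching goal as helping to decide whether rescue surgery should be performed. Sensitivity alone does not answer that, because the risk left after negative biopsies also depends on how common residual tumor is. Section 8.7 recognises this and compares that risk with operative mortality, but no listed parameter or analysis delivers the comparison.

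**Working it through.** **Inputs.** Null 0.90, alternative 0.95, alpha 0.05, power 0.80, 194 patients with residual tumor, prevalence 10 to 30% (average 20%) and specificity near 100%, all from section 4.4. Mortality at 90 days of 2.8% overall and 12% at age 70 and above, from section 1. Section 4.4 does not state sidedness; one-sided is assumed because it reproduces the protocol's figure.

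**1. The protocol's own figures.**
n = [(1.645·√(0.90·0.10) + 0.842·√(0.95·0.05)) / 0.05]² = 183.3, so 184. A two-sided 0.05 would give 239. By the exact binomial, n = 194 gives alpha 0.043 and power 0.824. Then 194/0.90 = 215.6, so 216, and 216/0.20 = 1080. All stated figures are reproduced, and they belong to a test against 90%.

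**2. What success means.** The smallest count c with P(X ≥ c | 194, 0.90) ≤ 0.05 is 182, and 182/194 = 93.8%. The exact one-sided 95% lower bound is 90.2%; the exact two-sided 95% interval is 89.4 to 96.8%.

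| True sensitivity | P(X ≥ 182) |
|---|---|
| 90% | 0.043 |
| 91% | 0.102 |
| 92% | 0.216 |
| 93% | 0.395 |
| 94% | 0.618 |
| 95% | 0.824 |

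**3. What testing the stated minimum would take.** Against 95%, 194 patients need 190 positives (97.9%). The protocol gives no true value above 95%, so a range is assumed. Power would be 0.31, 0.65 and 0.95 at a true 97%, 98% and 99%. The smallest exact n for 80% power would be 601, 234 and 124.

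**4. Post-test risk.** With prevalence v, sensitivity s and specificity taken as 100%, the risk of residual tumor after negative biopsies is v(1−s) / [v(1−s) + 1−v].

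| Sensitivity | v = 10% | v = 20% | v = 30% |
|---|---|---|---|
| 95% | 0.55% | 1.23% | 2.10% |
| 90% | 1.10% | 2.44% | 4.11% |
| 70% | 3.23% | 6.98% | 11.39% |

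At 70% sensitivity the risk is above 2.8% and below 12% over the whole range. To bring it down to 2.8%, sensitivity would have to be about 74%, 88% and 93% at prevalence 10%, 20% and 30%. The same sensitivity can therefore fall on either side of operative mortality, depending on prevalence and age.

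**5. Table 1.** P(reaching the limit) at a single evaluation, if the true sensitivity is exactly the value tested:

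| Patients | Limit | Against 90% | Against 95% |
|---|---|---|---|
| 20 | 19 | 0.39 | 0.74 |
| 60 | 59 | 0.014 | 0.19 |
| 100 | 97 | 0.0078 | 0.26 |
| 160 | 155 | 0.0009 | 0.18 |
| 180 | 173 | 0.0020 | 0.32 |

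Over all nine rows the smallest value against 90% is the 0.0009 at 160 patients. No row gives an error below 0.0005 against either value. If the limits are read as counts to be exceeded, only the row at 160 patients falls below 0.0005 against 90% (0.00024), and none does against 95%. These figures are per evaluation; the extra requirement of reaching the limit twice is not modelled.

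**The case against.** The strongest defence is that nothing is hidden. The margin is pre-stated in the same paragraph, the null and alternative are placed openly at 0.90 and 0.95, and the size matches. Non-inferior to 95% with a 5-point margin means above 90%, so success at a true 92 to 94% is ordinary power inside an accepted margin. At 90% the exact error is held at 4.3%. This stands as a defence of the test and its size. It does not reconcile the margin with the sentence that makes 95% the minimum. The reason offered, that exact equality to 95% cannot be proved, does not require a margin either, since a minimum of 95% can be tested directly with 95% as the null (step 3).

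A reader might infer that the protocol sets three incompatible bars: 95%, 90% and 70%. The text does not support this. The 70% is an example in an argument against stopping for low sensitivity, limited to high-risk groups, and the protocol's own figures bear it out: 3.2 to 11.4% against the 12% quoted for age 70 and above.

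A reader might also infer that the sensitivity test and the section 8.7 reasoning give harmfully opposite answers. That is weak. At the average 20% prevalence, 93% sensitivity gives 0.20·0.07/(0.20·0.07 + 0.80) = 1.7%, below the 2.8% overall mortality. The unfavourable direction, where biopsies can pass the test while post-test risk exceeds mortality, appears only at 30% prevalence, as 2.9% against 2.8%. That gap is too small to matter between rough estimates.

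Finally, section 8.1.2 records mortality with competing risks in mind, and an analysis plan that is not shown might tabulate predictive values. That is fair for the tabulation. It does not explain why the protocol's own lists of objectives and parameters omit the quantity on which section 8.7 rests.

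**Conclusion.** The point holds for the meaning of a positive result. The rule implied by section 4.4 can declare success with probability 22%, 39% and 62% at a true sensitivity of 92%, 93% and 94%, all below the protocol's stated minimum. What success supports is a sensitivity above 90% (lower bound 90.2% at the threshold count of 182). This assumes a one-sided exact test at 0.05 with 194 evaluable patients. The sample-size arithmetic is not at fault.

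It also holds that post-test risk and negative predictive value carry the argument in section 8.7 without being an objective, parameter or analysis. The post-test figures above assume a specificity of 100% and the protocol's own prevalence and mortality estimates. Which sensitivity is clinically sufficient is not judged here; the point is that the passages must be reconciled.

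**What to change.** 1. **Section 4.4.** Reconcile the 95% sentence with the test: name 95% as the expected (design) value and 90% as the tested performance goal. Word a positive conclusion as sensitivity exceeding 90%, with its exact lower bound. The 194 stays. If the sponsor prefers to keep 95% as a true minimum, it has to become the null, with the sizes shown in step 3.
2. **Table 1 in section 8.7.** Bring the caption into line with the same goal only together with recalculated limits. Rewording alone would attach an error rate of 0.0005 to limits that do not deliver it.
3. **Sections 8.1.2 and 10.** Add the probability of residual tumor after negative biopsies (1 minus the negative predictive value) with an exact confidence interval. Report it beside the observed 90-day mortality, overall and by age, without prescribing a clinical threshold.

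The cost is protocol wording, a recalculation of Table 1 and one extra table from data already collected. No patients or procedures are added. The drawback is a slightly less favourable headline claim.

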## **5 Treatment of subjects**

Not applicable

### 5.1 Investigational product

Not applicable

### 5.2 Use of co-intervention

Not applicable

### 5.3 Escape medication

Not applicable

## **6 Investigational product**

Not applicable.

## **7 Non-investigational product**

Not applicable

## **8 Methods**

### 8.1 Study parameters/endpoints

#### 8.1.1 Main study parameter

The sensitivity of endoscopic biopsies from the polypectomy-site for residual adenocarcinoma, as compared to the surgically resected specimen.

#### 8.1.2 Secondary study parameters

The postoperative mortality of the surgical resection (for the purpose of a possibly incompletely removed malignant polyp), as occurring within 91 days after surgery, irrespective of the cause of death as well as of the relation to the surgery (in order to evaluate competing risks).

### 8.1.3 Other study parameters

The following parameters will be recorded:

#### 8.1.3.1 General information

- Center name, name of treating physician
- Gender, date of birth, initials, first letter of family name.
- Comorbidity according to the American Association of Anesthesiology (ASA status).
- Has the patient an elevated risk of having Lynch syndrome?

#### 8.1.3.2 Data from endoscopic procedure during which the malignant polyp has been removed

- Date of the procedure.
- Estimated location of the tumor (distal rectum (before the first haustric fold), proximal rectum (proximal to the first haustric fold, but within 15 cm of the anal verge), sigmoid, descending colon, splenic flexure, transverse colon, hepatic flexure, ascending colon, cecum.
- Distance from the anal verge, measured during withdrawal of the endoscope. Distance is estimated using the centimeter scale on the shaft of endoscope
- Endoscopically estimated size of the polyp as compared to a closed snare (3 mm) or opened biopsy forceps (7 mm).
- Expected pathology (adenoma, serrated adenoma, carcinoma).
- Polyp shape according to Paris.
- En-bloc resection.
- Use of a snare.
- Use of submucosal injection.
- Use of electrosurgical current.
- Tattoo.
- Estimated endoscopic radicality.
- Circumferential incision (partial or complete).
- Submucosal dissection.
- Bleeding (immediate or delayed).
- Perforation (immediate or delayed).
- Intervention for complication (endoscopic, angiographic, surgical).

- Severity of complication according to the standard of the dutch association of gastroenterology.

*Advanced characteristics (not obligatory):*

- Presence of spontaneous bleeding
- NICE- and Hiroshima-classification.
- Pit-pattern according to Kudo.
- Lifting classification graded according to Kato.

#### 8.1.3.3 *Pathology of the endoscopically removed malignant polyp*

- T-number.
- Date of the report.
- Specimen: en-bloc or fragmented.
- Size of the (largest) fragment.
- Primary lesion: hyperplastic polyp, tubular adenoma, tubulovillous adenoma, villous adenoma, traditional serrated adenoma, sessile serrated lesion, with invasive malignancy.
- Finding: with low-grade dysplasia, with high-grade dysplasia, suspicion of carcinoma, with invasive malignancy, with pseudo-invasion
- Tumor type: adenocarcinoma, other.
- Differentiation grade: well, moderate, poor.
- Depth of invasion.
- Resection margin (free, not free of tumor, unable to judge, ....mm).
- Lymphovascular invasion (yes, no, unable to judge).

*Additional pathology findings (not obligatory).*

- Tumor budding.
- Haggit Level.
- Kikuchi Level.

#### 8.1.3.4 *Data from biopsies from the polypectomy site (second investigational endoscopy)*

- Date of the endoscopic procedure.
- Type of procedure (sigmoidoscopy or colonoscopy).
- Finding: scar, tattoo, ulcer, polypous remnant, suspicion of residual cancer, no reliable identification of the polypectomy site.
- Number of biopsies.
- Bleeding (immediate, delayed).
- Perforation (immediate, delayed).

- Intervention for complication (endoscopic, angiographic, surgical).
- Impact of complication on scheduled surgical resection: no change, antedation, postponation, cancellation.
- Severity of complication according to the Dutch Society of Gastroenterology.

#### 8.1.3.5 *Pathology of scar biopsies*

- T-number.
- Date of pathology report.
- Number of biopsies.
- Primary finding: normal mucosa, granulation tissue, ulcer, scar tissue, low-grade dysplasia, high-grade dysplasia, suspicion of carcinoma, invasive carcinoma.
- Type of tumor: adenocarcinoma, other.

#### 8.1.3.6 *Data from the surgical intervention or endoluminal full-thickness resection*

- Date of the operation.
- Type of operation: TEM, TAMIS, eFTR, abdominoperineal resection, low anterior resection, sigmoid resection, Hartmann procedure, left hemicolectomy, transverse resection, right hemicolectomy, ileocecal resection, total proctocolectomy, subtotal colectomy.
- Ostomy: temporarily, definitive.
- Conversion to open procedure.
- Complications (within 93 days): Anastomotic leakage, rebleeding, abdominal sepsis, other infection, relaparotomy, deceased.
- Intensive care ....days.

#### 8.1.3.7 *Pathology of the surgical specimen*

- T-number.
- Date of the pathology report.
- Tumor present.
- Type of tumor: adenocarcinoma, other.
- Differentiation grade: well/moderate, poor, unable to judge.
- Depth of invasion: intramucosal, lamina propria, submucosal, muscularis propria, pericolic fat / tissue, peritoneal surface, other organ.
- Angioinvasion: not found, lymphatic vessel, venous invasion.
- Total number of lymph nodes in the resected specimen.
- Number of lymph nodes with metastases.

- Number of lymph nodes with isolated tumor cells.

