## 8.3 Study procedures

### 8.3.1 Investigational endoscopy

For the purpose of the study, preoperative biopsy of the polypectomy site will be done. To allow for sufficient healing of the polypectomy site, an arbitrary period of at least 14 days will exist between the endoscopic resection of the malignant polyp and the second endoscopy. In daily practice, however, it is hard to imagine that the time interval between the two endoscopies could be shorter. First, the pathology report has to be completed, the patient has to be informed, dissemination studies have to be arranged, and the results have to be discussed in a multidisciplinary oncological meeting. If no dissemination has been found and additional resection has been decided on, the patient has to be seen by the surgeon for final planning of the operation. Only after this moment, participation in the study can be offered. The time between the biopsies and surgery should not exceed 4 weeks.

It is convenient to take biopsies from the polypectomy site when a second endoscopy is done for tattooing the polypectomy site or during endoscopic full-thickness resection. In this situation, the burden of participation in the study is zero.

If tattooing has already been done during the first endoscopy (when the malignant polyp was removed), a second endoscopy has to be arranged for the sole reason of participation in the study.

If the malignant polyp was located in the recto-sigmoid colon, a sigmoidoscopy will suffice. Otherwise, the colonoscopy has to be repeated. The details of these investigations are explained in the patient information form. Of course, it remains the decision of the patient whether or not to participate in case a separate endoscopy needs to be arranged. It should be realized, that the patient recently underwent a colonoscopy, so he or she is “experienced” and this is an optimal situation to decide whether or not to participate. It should be kept in mind, that in back-to-back colonoscopy studies, new polyps have been found in 10-25% of cases. This extra colonoscopy check may be of advantage for the patient.

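### The specimen data do not show whether the polypectomy site was found, so where biopsies and specimen share one localisation a site error hides a false negative and biases sensitivity upward

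*Protocol*

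**What the plan says.** **Reference side.** Protocol 8.1.3.7 lists "Tumor present", then tumor type, grade, depth, angioinvasion and lymph nodes. Neither that list nor the operation items in 8.1.3.6 ask whether the scar, tattoo or polypectomy site was found. The independent pathology assessment in 8.3.3 is blind to the clinical situation, and no site check is described.

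**Endoscopy and biopsy side.** Site information is collected here. A tattoo is recorded at polypectomy (8.1.3.2). Scar, tattoo or "no reliable identification of the polypectomy site" is recorded at the second look (8.1.3.4), and scar tissue in the biopsies is recorded in 8.1.3.5. No evaluability or analysis rule uses any of these.

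**Timing.** Section 8.3.1 considers it convenient to take the biopsies "when a second endoscopy is done for tattooing the polypectomy site or during endoscopic full-thickness resection".

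**Analysis.** Section 10 divides the patients with positive biopsies by the patients with tumor in the bowel wall and/or nodes. A patient counts as evaluable if biopsies and a specimen are both available.

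**Target.** Section 4.4 says: "We state that sensitivity should be at least 95% to be clinically relevant". It adds that "a pre-stated margin of non-inferiority of -5% (90% in our study) is accepted".

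**The concern.** A tumor-free specimen shows that there was no residual tumor only if the specimen contained the place where the polyp had been. The protocol foresees that the site may not be found at the second look, but has no matching item for the specimen.

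This matters most when the biopsies and the specimen depend on the same judgement of where the site is. In same-session eFTR, a wrong localisation puts both samples in the wrong place. The same may happen when a tattoo placed at the second look guides a later local excision. A residual tumor then goes undetected by both, the patient is classed as a true negative, and a false negative drops out of the denominator. In that setting the error can only raise the sensitivity estimate.

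The study is meant to inform whether rescue surgery is performed (4.4), so overstated sensitivity is the harmful direction. At the planned size, few false negatives separate success from failure.

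**Working it through.** **1. The plan's own figures.** Null sensitivity is 0.90 and the alternative 0.95 (4.4). Power is 0.80, and alpha, described as "a probability of falsely accepting biopsies as non-inferior", is 0.05. Sidedness is not stated.

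- One-sided normal approximation: n = [(1.645·√(0.90·0.10) + 0.842·√(0.95·0.05)) / 0.05]² = 183.3, so 184. This matches "184 patients need to be included to achieve a power of 0.80". A two-sided alpha would give 239.
- Adding a continuity term 1/(2·0.05) = 10 gives 193.3, so 194, which matches "Using binomial distributions, it can be shown that 194 patients need to be included to achieve this goal".
- 194/0.90 = 215.6, so 216, and 216/0.20 = 1080. Both agree with 4.4.

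**2. Pass limit.** The protocol states none. The exact one-sided limit for n = 194 is reconstructed here as at least 182 positives (93.8%). Its false-acceptance risk at 0.90 is 0.0427 and its power at 0.95 is 0.824. At most 194 − 182 = 12 false negatives are allowed.

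**3. Effect of hidden false negatives.** Let h be the share of biopsy-missed tumors that the specimen also misses (assumption). Then

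observed sensitivity = Se / [Se + (1 − Se)(1 − h)].

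At Se = 0.90 the share of all residual-tumor patients hidden is 0.10·h.

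| h | Share of all tumor patients hidden | Observed sensitivity | P(≥182/194) |
|---|---|---|---|
| 0 | 0 | 0.900 | 4.3% |
| 2% | 0.2% | 0.902 | 5.0% |
| 5% | 0.5% | 0.905 | 6.4% |
| 10% | 1.0% | 0.909 | 9.5% |

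The hidden share equals f·e. Here f is the proportion of tumor patients whose biopsies and specimen share a localisation, and e is the chance that this localisation is wrong. The three non-zero rows arise, for example, from f = 10% with e = 2%, 5% and 10%. The protocol gives neither f nor e.

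**4. In counts.** At the limit, 182/194 has exact p = 0.043 against 0.90. Restoring one hidden false negative gives 182/195 = 93.3%, p = 0.070. Restoring three gives 182/197 = 92.4%, p = 0.159.

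**5. The formula as written.** Under section 10, a biopsy-positive patient whose specimen missed the site enters the numerator but not the denominator. Suppose 194 patients have tumor in the specimen, 182 of them biopsy-positive, and there is one such extra patient. The written formula gives 183/194 = 94.3%. With that tumor counted in both places the result is 183/195 = 93.8%. Restricting the numerator to patients with tumor in the specimen gives 182/194 = 93.8%.

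**6. Where the bias does not arise.** If a separate resection contains the true site and the biopsies were taken elsewhere, the tumor is found and counted as a false negative. If the specimen misses the site independently of the biopsy result, true positives and false negatives are lost in proportion, and a proper two-by-two estimate is unbiased.

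**The case against.** Three arguments against the point carry weight.

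- **The affected subset may be small.** Of the 13 operation types in 8.1.3.6, 10 are segmental or larger bowel resections. Section 10 also counts nodal tumor as reference-positive, which keeps some patients in the denominator. A reader might infer that every site error inflates the estimate, whatever the operation. The documents do not support that, as step 6 shows.
- **Localisation is not ignored.** Tattooing is described in the Summary, 8.3.1 and 11.2, and site findings are recorded in 8.1.3.2, 8.1.3.4 and 8.1.3.5. These items are useful in analysis, but they record the endoscopist's own localisation and the biopsies, not the content of the specimen.
- **The information may be recoverable.** The pathology number and report date are kept (8.1.3.7), all pathology is to be independently assessed (8.3.3), and source data are held for 20 years (12.1). Permanent loss is therefore not shown. Whether routine reports mention the site cannot be judged from the documents.

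A reader might also take a much larger effect from the formula: h = 50% gives a false-acceptance risk of 78%. That would hide 5% of all tumor patients. It would need half of the shared localisations to be wrong if they made up 10% of tumors, or one in six if they made up 30%. Nothing in the protocol supports such rates.

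Finally, the extra sensitivity analyses could sit in a statistical analysis plan. The specimen item and the evaluability rule, however, are fixed in the protocol itself.

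**Conclusion.** The point holds in a limited form. No specimen item shows that the polypectomy site was present, and section 10 accepts any specimen as the reference. The upward bias is firm for same-session eFTR, where biopsies and specimen share one localisation. It is possible for local excision guided by a tattoo placed at the second look. It is not established for the other operations, apart from the numerator problem in the written formula.

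The size cannot be derived from the documents. The illustrative rise from 4.3% to between 5.0% and 9.5% rests on the assumed h, a true sensitivity of 0.90 and the reconstructed limit of 182/194. The count result needs no assumption about h: at that limit, one hidden false negative is enough to lose significance at 0.05. This is a cheap improvement worth making, not a defect that invalidates the design.

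**What to change.** 1. **Data item.** Add to 8.1.3.7, taken from the pathology report: *polypectomy site (scar/tattoo) identified in the specimen: yes / no / not assessable*.
2. **Reference rule.** In section 10, class a tumor-negative specimen without an identified site as an unverified reference, not as tumor-free.
3. **Numerator.** Count only biopsy-positive patients with tumor in the specimen. List biopsy-positive patients with a tumor-free specimen separately.
4. **Sensitivity analysis.** Report sensitivity also without same-session biopsy-plus-eFTR patients. They can be identified from the procedure dates in 8.1.3.4 and 8.1.3.6 and the operation type.
5. **Bound.** Add to the false negatives those expected among unverified biopsy-negative patients, at the residual-tumor risk observed in verified biopsy-negative patients. Overall prevalence is the wrong rate. At 20% prevalence and perfect specificity, the risk after a negative biopsy is 0.02/0.82 = 2.4% at sensitivity 0.90 and 0.01/0.81 = 1.2% at 0.95. Because that risk may be too low where the site was missed, add a worst case labelled as such.

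The cost is one case-report field and two supplementary analyses, with no extra patients or procedures. The downside is that a few reference-negatives become unverified; how many is unknown.
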